## Section G: Sample Size/Data Analysis

### G1. Sample Size

How many subjects (or specimens, or charts) will be used in this study?

Local: 50      Worldwide: 50

Please indicate why you chose the sample size proposed:

Phase I: does not involve participants. We plan to recruit 5 participants for phase II and 30 participants for phase III. To account for a 40% drop out rate the PI evidenced in a prior study using Video telehealth, we will over recruit for phase II and phase III. Recruitment feasibility of approximately 6 subjects per month is based on the number of participants from [name] VSTOP study who also had comorbid psychological distress. The study is underpowered to show clinically meaningful efficacy of *I'm Whole* when compared to usual care.

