In Phase II: The PI will pilot IM Whole by treating 5 Veterans suffering from stroke and comorbid psychological distress. Five Veterans with stroke and comorbid psychological distress will be recruited from the stroke acute care unit, rehabilitation unit, and outpatient stroke follow-up clinic. Qualitative interviews asking the Veterans opinion regarding the treatment content and delivery method will be administered at the end of the final session.

In phase III: Interested Veterans will be randomized to IM Whole (n=15) or usual care plus education (UC+E) (n=15), respectively. Veterans in the UC+E group will receive standard acute care, rehabilitation unit or

outpatient follow-up clinic stroke treatment provided at the MEDVAMC. The standard of care for these patients consists of appointments in the outpatient stroke follow-up clinic, medication management for comorbid chronic diseases, and general physical rehabilitation exercises. To account for additional treatment contact provided to participants in I'm Whole, UC+E will also receive 6 brief telephone calls with information regarding unrelated health topics (e.g., breast, colon, rectal, esophageal, skin and testicular cancer treatment and prevention). We will track the number of patients screened, number and percent of patients eligible, number randomized, number and percent completing treatments, and number and percent completing subsequent follow-up assessments following treatment completion. Veterans in I'm Whole will complete the same qualitative interviews described in phase II.

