Phase II and Phase III: Screening and Recruitment Procedures. We will recruit men and women Veteran stroke patients of all races and ethnicities with depression and anxiety symptoms who are being treated in the stroke acute care inpatient unit, rehabilitation unit, or outpatient stroke follow-up clinic at the Michael E. DeBakey VA Medical Center (MEDVAMC). The MEDVAMC treats over 310 Veterans with stroke each year, of which approximately 93 (33%) have comorbid psychological distress. We have successfully recruited Veteran stroke patients in our previous stroke studies. The research assistant (RA) will approach potential participants at bedside in the acute or rehabilitation unit or during the first follow-up visit after admission from the stroke acute care unit. Veterans interested in the study will be screened for eligibility via their electronic medical records (EMR) to see if they meet preliminary study inclusion/exclusion criteria (listed above). Those who meet the eligibility criteria will receive a follow up session, in their home or at the MEDVAMC to be administered the screening measurements listed above. If participants via EMR review or baseline assessments: 1) do not demonstrate or show evidence of a cognitive impairment, as evidenced by a score of >3 on a brief cognitive screener; 2) have a documented diagnosis of psychotic disorder or schizophrenia; 3) score in the severe range for depression, or anxiety (based on PHQ-8 or GAD-7 score of > 20), or have a documented or self-reported hospitalization for psychiatric illness within the past 30 days, they will be invited to participate in the study. They will be provided instructions regarding using VTEL to conduct their sessions, given a *I'm Whole* workbook and scheduled a time for first session with the study clinician. A note will be placed in the electronic medical records (EMR)s documenting the visit. Participants who do not meet the criteria will be immediately notified of their ineligibility. A note will be placed in the EMR documenting why they were not eligible. Their primary care provider will be signed to the note for follow up discussion regarding possible referrals or additional services needed for the Veteran. The Veteran will also be provided a list of community based psychiatric and medical resources.

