### G2. Data Analysis

Provide a description of your plan for data analysis. State the types of comparisons you plan (e.g. comparison of means, comparison of proportions, regressions, analysis of variance). Which is the PRIMARY comparison/analysis? How will the analyses proposed relate to the primary purposes of your study?

We hypothesize that, at 12 weeks posttreatment, Veterans randomized to I2m Whole will show greater improvements in the primary outcome (QoL) and secondary outcomes (PF, physical activity, SRF and psychological distress). On the basis of retention rates for VSTOP trials using VT, we anticipate a 20% loss-to-follow-up rate at 12 weeks post-treatment. Initial analyses will be intention-to-treat. Analyses will be repeated using the observed data (completer analyses). We will run linear regression models. The model for each outcome will include treatment, time (baseline, posttreatment, and 12 weeks post-treatment) and treatment-by-time interaction. Significant interaction will indicate that the intervention groups showed differential improvement over time. We will use SAS PROC MI and PROC MIANALYZE to impute missing data and conduct analyses. Key demographic and clinical variables (e.g., age, gender, stroke, psychological symptom severity and psychotropic medication use) will be described for each group as recommended by the CONSORT statement for RCTs. We will calculate the effect size, d, at post-treatment and at 12 weeks posttreatment, using mean values from the estimated means and standard errors from the linear model analyses of the imputed datasets.

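### At the 40% drop-out that G1 sets out to cover, its total of 50 leaves about 30 participants, not the planned 5 + 30 = 35; keeping 35 would need 59.

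*Combined protocol and SAP*

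**What the plan says.** Section G1 (Sample Size) answers the question of how many subjects will be used with 50, both locally and worldwide. The base plan is: "We plan to recruit 5 participants for phase II and 30 participants for phase III". The step from 35 to a larger number is justified by attrition: "To account for a 40% drop out rate the PI evidenced in a prior study using Video telehealth, we will over recruit". G1 applies this to both phases: "we will over recruit for phase II and phase III". It gives no inflation formula and does not divide the 50 by phase or arm. It also states that the study is underpowered for efficacy.

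Section F1 (Design) describes Phase III with the base numbers: "Interested Veterans will be randomized to IM Whole (n=15) or usual care plus education (UC+E) (n=15), respectively". It also lists the feasibility counts to be tracked, including "number randomized, number and percent completing treatments, and number and percent completing subsequent follow-up assessments".

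Section G2 (Data Analysis) uses a different attrition figure, taken from the VSTOP trials: "we anticipate a 20% loss-to-follow-up rate at 12 weeks post-treatment".

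**The concern.** A target of 35 is over-recruited for a stated 40% drop-out, so the resulting total should leave about 35 after 40% are lost. It leaves 30. G1 is where the plan explains its sample size, and the reason given there does not produce the number given.

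The stakes are those of a pilot. Nothing in the plan's power position changes, since none is claimed. But numbers randomised, completing treatment and completing follow-up are explicit outputs of this study, and G2 plans a completer analysis and effect sizes. If 40% holds, Phase III will probably finish below 15 per arm. Because the 50 is not split, nobody can see this from the plan. Study staff also cannot tell from F1 and G1 together how many to randomise: F1 gives 30, while G1 implies more without saying how many more.

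**Working it through.** **Inputs.** Phase II target 5 and Phase III target 30 (G1), so T = 35. Drop-out d = 0.40 (G1). Stated total N = 50 (G1). Phase III allocation 15:15 (F1). Alternative loss rate 0.20 (G2). Recruitment rate about 6 per month (G1).

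**1. Can 50 be reproduced?** To keep T after a fraction d is lost, enrol N = T/(1 − d).

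- Correct form: 35/(1 − 0.40) = 58.3, rounded up to 59. This is not 50.
- By phase: 5/0.6 = 8.3, so 9; 30/0.6 = 50 (25 per arm). 9 + 50 = 59, the same total.
- Multiplying by 1 + d: 35 × 1.4 = 49, close to 50. This common slip may be the source, but G1 shows no formula, so that is inference.
- Phase III alone: 30/0.6 = 50 exactly. That leaves no places for Phase II, which G1 says is over-recruited too. Even an uninflated Phase II would make the total 50 + 5 = 55.

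**2. What 50 yields.**

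| Drop-out | Expected to remain of 50 | Against 35 |
|---|---|---|
| 40% (G1) | 50 × 0.6 = 30 | 5 short |
| 30% | 50 × 0.7 = 35 | break-even, 1 − 35/50 |
| 20% (G2) | 50 × 0.8 = 40 | 5 over |

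Treating drop-outs as independent, the number retained is binomial. P(at least 35 of 50 remain, retention 0.6) = 0.096. At retention 0.8 the same probability is 0.969.

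**3. What this means for Phase III at 40%.** The plan gives no split, so two are shown.

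| Phase II enrols | Left to randomise | Expected completers | Per arm | P(at least 30 complete) |
|---|---|---|---|---|
| 9 (to keep 5) | 50 − 9 = 41 | 41 × 0.6 = 24.6 | 12.3 | 0.057 |
| 5 (not inflated) | 50 − 5 = 45 | 45 × 0.6 = 27 | 13.5 | 0.22 |

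Both fall below 15 per arm.

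**4. Cost of the larger total.** (59 − 50)/6 = 1.5 months of extra recruitment.

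**5. A separate slip in the recruitment pool.** Section F2 says that of more than 310 stroke patients a year, "approximately 93 (33%) have comorbid psychological distress". But 93/310 = 30.0%, and 33% of 310 is 102. The result above does not depend on this.

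**The case against.** The arithmetic is not in dispute. The objections concern how G1 is read.

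- **No retained number is stated.** G1 speaks of recruiting 5 and 30, and never says that 35 must complete. That is true, and 35 as the number to keep is an inference. But over-recruiting to allow for drop-out has no other purpose, and if 35 were simply the number enrolled, the total of 50 would have no explanation.
- **What 50 counts is undefined.** It could be a ceiling on consents that includes people lost before randomisation. This is possible, but it would leave fewer than 50 exposed to the 40% loss and so would widen the gap.
- **The 40% comes from a video-telehealth study, and the control arm receives telephone calls.** Inflating only the 20 video-treated participants gives 20/0.6 = 33.3, so 34, plus 15 controls = 49, which fits within 50. That requires no loss at all among controls. With G2's 20% for controls, 15/0.8 = 18.75, so 19, and the total is 34 + 19 = 53, which is still above 50. G1 makes no distinction by arm.
- **G2's 20% removes the shortfall.** At that rate it does. But G1 names 40% as the rate it covers, and the two figures are not related to each other anywhere.
- **The main analysis is intention-to-treat with multiple imputation, and the study is declared underpowered.** This stands and limits the consequence: completers are not the analysis set for the first analysis, and no power, alpha or effect size rests on 50.

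What remains of the other side is that the harm is modest and the source of the 50 is unproven. Neither point makes 50 consistent with G1's own reason for it.

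**Conclusion.** The concern holds. At G1's own rate, 50 enrolled gives 30 expected completers, 5 fewer than 35, with about a 10% chance of keeping 35 or more. Keeping 35 in expectation needs 59, which is 9 more than stated. Phase III would be expected to end with about 12 to 13.5 completers per arm, depending on whether Phase II enrols 9 or 5.

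This rests on three readings: 50 counts people enrolled, 35 is the number to be kept, and the 40% applies to both phases and both arms. The probabilities also assume independent drop-outs. At a loss of 30% or less there is no expected shortfall.

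The sponsor should correct this, but it does not threaten the study: the error is in the expected yield of a pilot, not in a power claim.

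**What to change.** Keep 50 and make the text agree with it:

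1. In G1, state the expected yield at 40% drop-out (about 30 completers) and how the 50 divides by phase and arm. One example is 9 enrolled in Phase II (9 × 0.6 = 5.4, so about 5 completers) and 41 randomised in Phase III (about 12 completers per arm).
2. In F1, replace 15 per arm with the over-recruited number to be randomised, or label 15 as the base before over-recruitment.
3. Add one sentence relating G1's 40% drop-out to G2's 20% loss to follow-up. F1 already tracks treatment completion and follow-up completion separately, so the two rates can be defined against those counts if that is what is meant.

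This costs no participants. The only price is that the stated yield reads less favourably: 30, not 35.

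If 35 completers are a requirement, the total becomes 59 (9 in Phase II, 25 per arm in Phase III). That adds 9 participants and about 1.5 months at 6 per month.

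As a separate clerical correction, make the count and percentage of distressed patients in F2 agree: 93 of 310 is 30%.

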### G2. Data Analysis

Provide a description of your plan for data analysis. State the types of comparisons you plan (e.g. comparison of means, comparison of proportions, regressions, analysis of variance). Which is the PRIMARY comparison/analysis? How will the analyses proposed relate to the primary purposes of your study?

We hypothesize that, at 12 weeks posttreatment, Veterans randomized to I2m Whole will show greater improvements in the primary outcome (QoL) and secondary outcomes (PF, physical activity, SRF and psychological distress). On the basis of retention rates for VSTOP trials using VT, we anticipate a 20% loss-to-follow-up rate at 12 weeks post-treatment. Initial analyses will be intention-to-treat. Analyses will be repeated using the observed data (completer analyses). We will run linear regression models. The model for each outcome will include treatment, time (baseline, posttreatment, and 12 weeks post-treatment) and treatment-by-time interaction. Significant interaction will indicate that the intervention groups showed differential improvement over time. We will use SAS PROC MI and PROC MIANALYZE to impute missing data and conduct analyses. Key demographic and clinical variables (e.g., age, gender, stroke, psychological symptom severity and psychotropic medication use) will be described for each group as recommended by the CONSORT statement for RCTs. We will calculate the effect size, d, at post-treatment and at 12 weeks posttreatment, using mean values from the estimated means and standard errors from the linear model analyses of the imputed datasets.

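### G2 states a 12-week QoL hypothesis but names only a three-visit interaction test, with no within-Veteran correlation stated and two dates for the final visit

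*Combined protocol and SAP*

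**What the plan says.** The form heading of Section G2 asks "Which is the PRIMARY comparison/analysis". The answer names QoL as the primary outcome and gives a directional hypothesis of greater improvement: "We hypothesize that, at 12 weeks posttreatment, Veterans randomized to" the intervention will do better.

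The analysis is then set out in three steps:
- **Model.** "We will run linear regression models". The terms are: "The model for each outcome will include treatment, time (baseline, posttreatment, and 12 weeks post-treatment) and treatment-by-time interaction".
- **Decision rule.** "Significant interaction will indicate that the intervention groups showed differential improvement over time". No other test is named, and no alpha is given.
- **Effect size.** "We will calculate the effect size, d, at post-treatment and at 12 weeks posttreatment", obtained by "using mean values from the estimated means and standard errors from the linear model analyses of the imputed datasets".

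No random effect, covariance structure or robust standard error appears in G2 or elsewhere in the document.

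On timing, Section F2 (Assessment Procedures) and Section L (Distribution Plan) place the three paid assessments at weeks 0, 6 and 12. Sections F1 and F2 give a treatment of six weekly sessions. G2 places the last assessment 12 weeks after treatment.

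**The concern.** The hypothesis concerns one time point, while the named test covers three visits at once. A significant interaction says that the arms' profiles differ somewhere. It does not say that they differ at the final visit, so a benefit that has vanished by then can give the result that G2 would read as differential improvement.

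Separately, each Veteran contributes three correlated scores to models described only as linear regression. If these are fitted as ordinary least squares (OLS) on stacked rows, stable differences between Veterans stay in the error term, and the standard errors of change contrasts are wrong.

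Section D makes preliminary data on the QoL effect an aim, and Section G1 declares the study underpowered for efficacy. The final-visit estimate and its interval are therefore the useful product, and G2 plans no interval for it.

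**Working it through.** **Inputs from the documents.** 15 per arm (Section F1); three visits; "we anticipate a 20% loss-to-follow-up rate at 12 weeks post-treatment", which takes 15 to 12 per arm. G2 states no power, effect size, SD or alpha, so there is no figure of the plan's own to reproduce.

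**Assumptions, not in the documents.** Two-sided alpha 0.05; SD 1 at every visit; equal correlation ρ = 0.3/0.5/0.7 between visits; effect 0.8 SD where present; complete data.

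**1. What the interaction can detect.** Let D be the between-arm differences at baseline, post-treatment and final visit. The 2-df interaction has noncentrality λ = (n/2) × Σ(D − mean D)² / (1 − ρ).
- Sustained effect, D = (0, 0.8, 0.8): Σ = 0.64 × 2/3 = 0.427.
- Post-treatment-only effect, D = (0, 0.8, 0): Σ = 0.64 × 2/3 = 0.427, the same.
- At n = 15, λ = 7.5 × 0.427/(1 − ρ) = 4.57/6.40/10.67. With 2 and 56 df, power is 44.6/58.9/82.0% for either pattern.
- At n = 12, λ = 3.66/5.12/8.53. With 2 and 44 df, power is 36.1/48.5/71.6%.

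The test cannot tell the two patterns apart. In the post-treatment-only case, the 1-df contrast of change to the final visit rejects about 5% of the time, as it should.

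**2. If the model is literally OLS (n = 15).**
- Difference in change from baseline to final visit: the OLS standard error is √(4/15) = 0.516, and the correct one is √(4(1 − ρ)/15). The ratio is 1/√(1 − ρ) = 1.20/1.41/1.83.
- 95% half-width: 0.516 × 1.989 = 1.03 SD under OLS (84 df), against 0.87/0.73/0.57 SD with the correlation modelled (56 df, t = 2.003).
- Power of that contrast for a sustained effect: 31/28/23% under OLS, against 44/58/79%.
- 2-df interaction by simulation: true size about 1.6/0.4/0.02% instead of 5%; power for a sustained effect 27/22/16%, against 45/59/82%.

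**3. The final-visit difference itself under OLS.** With equal variances the standard error is √(2/15) = 0.365 and the half-width is 0.365 × 1.989 = 0.73 SD, which is valid. OLS uses one variance averaged over the visits, so this fails if variances differ. With assumed SDs of 0.7/1/1, the averaged variance is (0.49 + 1 + 1)/3 = 0.83 against a true 1.00, and the simulated null rejection rate is 7.4–7.7%. With 0.7/0.9/1.1, it is 0.84 against 1.21, and rejection is about 10%. Unequal variance is plausible for the distress scores, because eligibility restricts them at baseline (Section F1).

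**4. The visit date.** Sections F2 and L end at week 12, and three payments of 20 dollars make the stated total of 60. G2 gives 6 + 12 = week 18. The only scheduled assessment after the post-treatment one thus has two dates.

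**The case against.** The strongest reply is that the needed quantity is already in the plan. G2's hypothesis is about improvement, that is, change. In the stated model, the between-arm difference in change to the final visit is one linear combination of the interaction coefficients, and G2 does plan a 12-week effect size from the model means. This stands. The gap is an unnamed primary contrast with no interval, not a missing estimate.

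A second reply is that linear regression may be loose wording for a mixed model. That is possible, and it removes step 2 of the working but not step 1, which holds for a correctly specified model. A third is that this is a pilot whose overall goal is to develop, refine and pilot the treatment, so power comparisons carry limited weight. That is fair, but G2 itself chose a hypothesis and a significance rule, and the two should match.

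Three stronger readings are tempting and are not supported:
- **That ignoring correlation inflates false positives in the named test.** The opposite holds: the OLS interaction is conservative. A time-averaged treatment effect from the same fit would reject too often, but G2 names no such test.
- **That the planned final-visit estimate is invalid.** It is not. Under OLS its standard error depends on equal variances across visits.
- **That the effect size is materially biased.** The standardising SD is not named, but that is a definition gap. The plausible choices shift d by little compared with its sampling error of about 0.4.

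**Conclusion.** The point holds and should be fixed before analysis. The named test does not answer the 12-week hypothesis under a correct model with visit as a factor. Under the stated assumptions, it is significant 45/59/82% of the time for an effect confined to post-treatment. The unstated correlation is a real gap in specification. Its cost (power 27/22/16% instead of 45/59/82%, and change standard errors 1.20 to 1.83 times too large) arises only if the models are fitted as OLS. The conflict over the visit date does not depend on any assumption.

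The percentages rest on the assumed 0.8 SD effect, ρ and complete data. Complete data is optimistic given the planned imputation and the losses that G1 and G2 expect.

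**What to change.** 1. Reconcile Sections F2 and L with G2 so that the final visit is one defined time.
2. In G2, replace the linear regression wording with a linear mixed model for repeated measures fitted to each imputed data set. Use baseline and both follow-ups as responses, visit as a factor, treatment-by-visit, an unstructured within-Veteran covariance and a small-sample df method such as Kenward-Roger.
3. Name as the primary comparison the 1-df between-arm difference in QoL change from baseline to the final visit, with its 95% CI. Keep the three-visit interaction as supportive only.

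Modelling follow-up scores with baseline as a covariate, or a constrained-baseline model, is an acceptable and more efficient alternative. In a model with follow-up scores only, the treatment-by-visit term compares just the two follow-ups. It is zero for a sustained effect and must not be read as the test of benefit.

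**Cost.** A few sentences and one agreed visit time, with the same data and the same SAS workflow (PROC MIXED between PROC MI and PROC MIANALYZE). The downside is a few degrees of freedom for the covariance parameters. With complete data, the change contrast would have 2 × 15 − 2 = 28 df instead of 56, so the t multiplier is 2.048 instead of 2.003, an interval about 2% wider.

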## **Section F: Design/Procedure**

### **F1. Design**

Select one category that most adequately describes your research:

c) Pilot

Discuss the research design including but not limited to such issues as: probability of group assignment, potential for subject to be randomized to placebo group, use of control subjects, etc.

IM Whole is a 6 session behavioral treatment that addresses psychological distress and stroke self-management behaviors that will be delivered via VT in the home. The treatment will be delivered weekly over 6 weeks. One module will be provided each session. The sessions will last approximately 30-45 minutes. The first module will combine the VSTOP-II stroke self-management education regarding stroke risk factors and EPIC psychoeducation on how comorbid psychological distress can create barriers to engaging in stroke self-management behaviors. Clinicians will work with each Veteran to establish individualized plans for psychological distress management and strategies for practicing tailored PF, physical activity and SRF behaviors in line with the Veteran's values. Progress towards the Veteran's tailored PF, physical activity and SRF behaviors will be reviewed, and psychological distress barriers will be discussed in future modules. Modules 2-5 will be electives that provide cognitive behavioral treatment (CBT) based behavioral activation, social-support, cognitive-restructuring, thought-stopping, deep-breathing, and problem-solving skills for improving psychological distress-related barriers to practicing established PF, physical activity and SRF behaviors. Module 6 consists of a relapse prevention plan for continued management of psychological distress. Homework and tracking logs will be provided at the end of each session. The Co-I, [name], will provide feedback during the development and refinement stages regarding creating tailored PF and physical activity strategies for participants. The Co-I, [name], will provide feedback in the development and refinement stages regarding client-centered strategies for reintegrating into family and community roles and activities poststroke. A clinician manual and patient workbook will be developed.

In phase I: The PI will work with the study team to combine the EPIC and VSTOP treatments into one cohesive treatment called IM WHOLE. No Veterans will be involved in this phase.

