## **F2. Procedure**

Phase I: The PI will merge stroke self-management and psychological distress treatment modules from their established EPiC and VSTOP-II programs. The first module will combine the VSTOP-II stroke self-management education regarding stroke risk factors and EPiC psychoeducation on how comorbid psychological distress can create barriers to engaging in stroke self-management behaviors. Clinicians will work with each Veteran to establish individualized plans for psychological distress management and strategies for practicing tailored PF, physical activity and SRF behaviors in line with the Veteran's values. Progress towards the Veteran's tailored PF, physical activity and SRF behaviors will be reviewed, and psychological distress barriers will be discussed in future modules. Modules 2-5 will be electives that provide CBT-based behavioral activation, social-support, cognitive-restructuring, thought-stopping, deep-breathing, and problem-solving skills for improving psychological distress-related barriers to practicing established PF, physical activity and SRF behaviors. Module 6 consists of a relapse prevention plan for continued management of psychological distress. Homework and tracking logs will be provided at the end of each session. [name] will provide feedback during the development and refinement stages regarding creating tailored PF and physical activity strategies for participants. [name] will provide feedback in the development and refinement stages regarding client-centered strategies for reintegrating into family and community roles and activities poststroke. The treatment will consist of 6 sessions over 6 weeks and will be delivered to Veterans in their homes, using VT technology. A clinician manual and patient workbook will be developed. There will be no Veteran involvement at this phase.

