In Phase II: The PI will pilot I'm Whole by treating 5 Veterans suffering from stroke and comorbid psychological distress. Five Veterans with stroke and comorbid psychological distress will be recruited from the stroke acute care unit, rehabilitation unit, and outpatient stroke follow-up clinic. The participants will receive each of the I'm Whole sessions using VT in the home. Sessions will be delivered weekly over 6 weeks. Clinicians will work with the Veteran to establish goals in the first session that will be reviewed through the remaining sessions. Qualitative interviews asking the Veterans opinion regarding the treatment content and delivery method will be administered at the end of the final session.

The barriers to receiving the intervention via VT and acceptability of the intervention content and procedures will be assessed informally after each session, and responses will be reviewed at weekly team meetings to address any unanticipated results and make needed immediate changes to the intervention. A semi-structured interview will occur with each Veteran post-treatment, conducted by the RA trained by Co-I [name], an expert in qualitative methods. Interviews will occur by phone and include open-ended questions regarding recruitment; engagement and retention strategies; assessment procedures; participant burden; redundancy and length and frequency of treatment; effectiveness, usefulness of I'm Whole content, and perceived benefits and barriers to receiving the sessions via VT to the Veteran's home. Detailed notes will be taken during interviews, which will also be audio recorded and transcribed for analysis. Rapid analysis is a systematic and rigorous process of condensing qualitative data to quickly identify key findings to inform study progress (i.e., refine and modify I'm Whole content, delivery methods and treatment procedures). The information from the transcribed notes and feedback received in weekly meetings will be used to modify the IM WHOLE treatment.

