Phase II and Phase III: Treatment Procedures and Development-- Sessions will be conducted by 1 clinician with master's-level training in health education, counseling or social work and expertise in CBT, psychological distress treatment, and/or chronic disease management. The clinician will conduct the sessions from the MEDVAMC using VA Video Connect VT to the Veterans in their homes. The MEDVAMC frequently uses VT for clinical treatment and research and has established VT programs and equipment that is VHA approved and readily available.

Assessment Procedures. Each participant in phase II and phase III will receive \$20.00 for each assessment they complete (0/6/12 weeks). Assessments will be conducted by an Independent Evaluator (IE). We estimate that each assessment will take about 30 to 40 minutes. If scores on the psychological distress measure worsen (e.g., 20% or more increase), the PI will be notified and participants referred to mental health treatment within the MEDVAMC or the community.

Phase III: This group will consist of the treatment (*I'm Whole* group) and usual care group will receive the standard of care. The standard of care for these patients consists of appointments in the outpatient stroke follow-up clinic, medication management for comorbid chronic diseases, and general physical rehabilitation exercises. To account for additional treatment contact provided to participants in *I'm Whole*, UC+E will also receive 6 brief telephone calls with information regarding unrelated health topics (e.g., breast, colon, rectal, esophageal, skin and testicular cancer treatment and prevention).

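### G2 puts the primary QoL hypothesis 12 weeks after treatment, but the 0/6/12-week visit schedule has no stated origin and, counted from baseline, ends about 6 weeks after treatment

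*Combined protocol and SAP*

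**What the plan says.** Section G2 (Data Analysis) uses the same late time point four times:

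- The hypothesis for QoL, the primary outcome, and for the secondary outcomes opens "We hypothesize that, at 12 weeks posttreatment, Veterans randomized to".
- On retention, "we anticipate a 20% loss-to-follow-up rate at 12 weeks post-treatment".
- On the model, "The model for each outcome will include treatment, time (baseline, posttreatment, and 12 weeks post-treatment) and treatment-by-time interaction".
- On effect sizes, "We will calculate the effect size, d, at post-treatment and at 12 weeks posttreatment".

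The visit schedule is given elsewhere. F2 (Assessment Procedures) says that participants are paid $20 "for each assessment they complete (0/6/12 weeks"), and the Distribution Plan in Section L repeats this. Neither place says what the weeks are counted from. Section L gives a total of $60.

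The length of treatment is consistent: "The treatment will be delivered weekly over 6 weeks" in F1, and "The treatment will consist of 6 sessions over 6 weeks" and "Sessions will be delivered weekly over 6 weeks" in F2. J2 places a baseline assessment after telephone consent. F1 also plans to count follow-up assessments completed after treatment, but attaches no week to them.

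**The concern.** The section that defines the analysis and the section that schedules the visits do not describe the same third visit unless the reader supplies an unstated change of clock. An evaluator who books visits from F2 would naturally read 0/6/12 as one sequence and see the participant at week 12. An analyst working from G2 would expect data from about week 18.

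The time point at stake is that of the primary hypothesis. If visits follow one clock from baseline, there are two possible outcomes. Either no QoL data exist at 12 weeks post-treatment, or data from about 6 weeks post-treatment are reported under the 12-week label. Neither can be repaired once the visits have taken place. The second effect size and the retention figure in G2 refer to the same visit and carry the same ambiguity.

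The control arm adds to the need for a stated origin. F1 and F2 give UC+E six short calls but no interval between them, so the end of treatment has no documented date in that arm.

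**Working it through.** **Inputs**

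- Treatment length: 6 weeks (F1, F2).
- Analysis time points: baseline, post-treatment, 12 weeks post-treatment (G2).
- Visit schedule: 0, 6 and 12 weeks, origin not stated (F2, Section L).
- Payment: $20 per assessment (F2, Section L), $60 in total (Section L).
- Assumption: treatment starts at about the time of the baseline assessment. F2 and J2 do not state the interval.

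**Step 1. Reproduce the plan's own figure.** 3 visits x $20 = $60, as in Section L. So there are three paid assessments, matching the three levels of time in G2.

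**Step 2. Weeks that G2 needs, from the start of treatment.** Baseline = 0. Post-treatment = 6. Twelve weeks post-treatment = 6 + 12 = 18. G2 therefore needs weeks 0, 6 and 18.

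**Step 3. One clock from baseline.** Visits fall at weeks 0, 6 and 12. The first two match G2. The third is 12 - 6 = 6 weeks post-treatment, which is 18 - 12 = 6 weeks earlier than G2 requires.

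**Step 4. Any other single clock.** If the clock starts at week s, visits fall at s, s + 6 and s + 12, so the first and last are always 12 weeks apart. The G2 points span 18 - 0 = 18 weeks. Shifting the origin cannot turn a 12-week span into an 18-week span, so no single origin gives all three G2 points. Counting from the end of treatment is in any case excluded, because G2 and J2 both require a baseline.

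**Step 5. A mixed clock.** If 0 and 6 are counted from baseline and 12 from the end of treatment, visits fall at weeks 0, 6 and 6 + 12 = 18. All three G2 points are met with three visits and $60.

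| Reading of 0/6/12 | Visits (weeks from start) | Third visit, weeks post-treatment | Agrees with G2 |
|---|---|---|---|
| One clock from baseline | 0, 6, 12 | 6 | First two points only |
| Mixed clock, not stated | 0, 6, 18 | 12 | All three points |

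Two readings remain, and they place the third visit 6 weeks apart.

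**The case against.** The strongest reply is that there is no real conflict. The 0/6/12 string appears only in parentheses beside a payment, whereas G2, which defines the analysis, is explicit and says the same thing four times. Three payments correspond one-to-one with three levels of time. On the mixed reading everything agrees and nothing needs to move.

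Much of this stands. The mixed reading is possible and may be what the sponsor meant. A reader might infer that the 12-week post-treatment visit has been left out of the study, and the documents do not support that: they leave its date open. The statement that no other schedule exists also holds only for the available text, since front pages and consent material are not shown.

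What does not stand is that the matter is settled. Nothing in F2 or Section L signals that the clock restarts between the second and third numbers, and the plain reading of such a string is a single sequence. The follow-up counts in F1 carry no week and so cannot decide between the two readings.

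It is also fair to say that the consequence is limited. G1 declares the study underpowered for efficacy, and this is a pilot.

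**Conclusion.** The point holds as an unresolved inconsistency in the timing of the primary hypothesis. On the single-clock reading, the third visit falls about 6 weeks post-treatment against 12 hypothesised, a shortfall of about 6 weeks. On the mixed reading the shortfall is zero. The available text does not say which applies.

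The 6-week figure rests on the stated 6-week treatment and on treatment starting close to baseline; a delay before the first session would shorten the follow-up further on the single-clock reading. That no single origin fits is less dependent on these assumptions: for any treatment of positive length, G2 needs a span longer than 12 weeks.

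Two stronger inferences should be resisted. A reader might conclude that the comparison between arms is compromised. It is not: the model can be fitted, and the randomised comparison at the third visit is valid whatever that visit is called. A reader might also take the ratio of 12 to 6 weeks as a measure of how far durability of benefit would be overstated. It is only a ratio of follow-up lengths, and the documents do not quantify durability.

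This should be fixed before visits are scheduled, as a clarification with a real consequence if left undone.

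**What to change.** Reconcile F2 and Section L with G2 by stating one calendar origin for both arms, namely the start of treatment or, in the control arm, the start of the UC+E calls. Then choose one of the following:

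- **Restate the schedule as weeks 0/6/18** in F2 and Section L. This keeps the hypothesis at 12 weeks post-treatment. The cost is a last visit 6 weeks later than week 12, or a wording change only if the mixed clock was always intended.
- **Keep 0/6/12 and relabel all four G2 references** as week 12 from baseline, about 6 weeks post-treatment. No visit moves. The cost is substantive, because the primary hypothesis then concerns a shorter follow-up.

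Both options keep three assessments and $60 per participant. G2 already ties the anticipated 20% loss to its last time point, so that figure needs no separate statement once the visit is dated and the label is consistent.
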